Final implant (NobelReplace® Conical) and respective bur diameter for either osseodensification instrumentation and conventional drilling will be either 3.5 mm, 4.3 mm or 5.0 mm. Implant lengths will be from 8.0 up to 13.0 mm. Versah (Fig. 2) and NobelReplace ® Conical implant surgical kit (Fig. 1) present burs with identical diameter and instrumentation will be performed so last bur diameter matches with chosen implant diameter. When using Versah, counterclockwise drilling will be performed in maxilla, and in mandible clockwise drilling. Before surgery, all patients will receive intraoral scans and will be subjected to tomographic examination of the edentulous site for virtual implant planning, surgical planning, implant selection, and fabrication of a surgical guide with a mark on the buccal aspect identifying the middle of the osteotomy. The osseodensification technique will be used for comparison with conventional drilling regarding ridge dimensional changes measured with a ridge caliber (Krekler Sliding Caliper Round Gauge Dental Instrument) at

implantation (T0); and insertion torque (IT) values and implant stability quotients (ISQ) at implantation (T0), 3 (T1,) 6 (T2), and at 12 weeks (T3). ISQ will be measured with Osstell ISQ meter. Data will be evaluated with paired t-tests. After T0, patients will receive a healing abutment which will be removed and repositioned for T1, T2, and T3 evaluations. After 12 weeks patients will be prosthetically restored if insertion torque was 35 Ncm and/or ISQ values are 68. After 6 months, follow-up tomographic examination will be completed for volumetric analysis.

Study Population

Patients of the Graduate Periodontology clinic requiring implant therapy will be screened and selected to participate in the study based on the following inclusion and exclusion criteria:

Inclusion Criteria

- Adults aged 22 years and older.
- Patients who understand and agree to this study.
- Adequate Oral hygiene
- One or more edentulous spaces, which are 10 weeks or longer after extractions
- Patients requiring signature from a Legally Authorized Representative (LAR) will be eligible to participate in the study

Exclusion criteria:

- Grafted extraction socket or ridge augmentation procedure utilizing xenogenic bone graft material.
- Pregnancy as checked via medical history
- Smoking of more than 5 cigarettes/day.
- History of alcoholism or drug abuse during the last 5 years.
- Uncontrolled Hypertension or diabetes.

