- Patient with malignant tumor.
- Patients on daily dose of steroids.
- Patients with history of chemotherapy or radiation for the last 12 months.

Study Procedures

Forty implants will be paired and placed in 20 patients using OsseoDensification (OD) protocol as test, and using standard drilling (SD) protocol as control. Sites will be randomly assigned in comparative patients prior to flap reflection.

Primary Outcome Measures:

All ridge dimensions will be measured immediately after flap reflection and after final osteotomy preparation: at crest, 5 mm and 10 mm apical from the crest. A surgical guide will be fabricated for the implant surgery which will also be marked on the buccal indicating the middle of the osteotomy and the ridge dimensions will be measured using the mark as a standard reference. The measurements will be completed the day of surgery only.

Secondary Outcome Measures:

1. All implants' primary stability will be measured by insertion torque values and by resonance frequency analysis (ISQ) immediately after implant placement (T0). Resonance frequency analysis will be measured at three weeks (T1), six weeks (T2), and twelve weeks (T3) post implant placement.
2. At 6 months all patients will receive CBCT for volumetric analysis.

Digital radiographs (periapical radiographs PA) will be taken prior to implant placement, post placement, and at 6 weeks. Cone beam computer tomography (CBCT) will be obtained prior to implant placement for implant planning and fabrication of a surgical guide, and at 6 months post-implantation for volumetric analysis.

In any incidence of less than 1 mm buccal plate thickness has resulted after bone preparation, bone grafting will be done post implant placement and complete implant coverage will be achieved for two-stage healing protocol. Cases requiring bone grafting will be excluded from the CBCT analysis at 6 months and from 3-week (T1) and 6-week (T2) ISQ readings. Cases requiring two-stage healing will also be excluded from 3-week (T1) and 6-week (T2) ISQ readings, but will be included in 12-week (T3) ISQ readings at second stage surgery.

At 12 weeks all patients will receive dental restorations. Implants' restorative phase will be initiated at any time resonance frequency analysis become equal or more than ISQ 68.

Why 3 weeks, 6 weeks, and 12 weeks ISQ measurements:

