1.2-D Linear CBCT analysis: we will superimpose the pre- and post- surgical CBCTs. Then determine a cross-sectional plane that goes through the long axis of the placed implant and is as perpendicular as possible to the buccal/lingual walls for consistent reproduction. We will use the selected cross-sectional plane to measure the overall buccolingual width of the ridge and assess any ridge dimensional changes. The software automatically finds the best fit for superimposition of the CBCT scan which allows for accurate reproducible measurements.

2.3-D Volumetric CBCT analysis: Superimposition of the CBCTs, as previously explained, will be completed first. A box will be used as the region of interest which will encompass the implant and the adjacent cortical plates. The shape of the box will be kept the same for consistency. The segmented ridge volume within the box will be used to get actual volumetric differences. The term segmentation is a radiology term and refers to the inclusion of voxels (in this case, alveolar process) that falls within a specified range of CBCT gray scale values determined by an operator.

Ethics

At the time of initial consult, all eligible subjects will be provided with the opportunity to decide if they want to participate in the study. A description will be provided as well as all that will be required by

the patient. If they agree to participate, a written consent form will be obtained, and the subject will be provided with a copy of the signed consent form. All consent forms will be kept by the Primary Investigator in a locked and secured place.

Data handling and record keeping

All participants will be identified by a number and all identifying information will be kept confidential. All the data will be collected in a spreadsheet (excel document) under the participant's specific number. Only the Primary Investigator will have access to the identifiable information linked to the subject's specific number which will be kept in a locked and secured cabinet in room 6477 in the Department of Periodontics and Dental Hygiene.

Quality control and assurance

[figure not shown]

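### The 3-D CBCT volume change does not treat the implant space the same way in both scans, so each site's change can be off by up to the implant's own volume

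*Combined protocol and SAP*

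**What the plan says.** Under Statistics & Computer tomography analysis, the 3-D volumetric item defines the measurement in three steps after the scans are superimposed.

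- Region: "A box will be used as the region of interest which will encompass the implant and the adjacent cortical plates".
- Constancy: "The shape of the box will be kept the same for consistency". No rule is given for the size or position of the box.
- Quantity: "The segmented ridge volume within the box will be used to get actual volumetric differences". Segmentation is explained as "inclusion of voxels (in this case, alveolar process) that falls within a specified range of CBCT gray scale values determined by an operator". The range is not given, and nothing says whether implant voxels are counted, left out or masked.

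Study Procedures fixes the timing. At baseline, "Cone beam computer tomography (CBCT) will be obtained prior to implant placement for implant planning and fabrication of a surgical guide"; the second scan is taken "at 6 months post-implantation for volumetric analysis".

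Surgical technique sets the sizes. The final implant diameter "will be either 3.5 mm, 4.3 mm or 5.0 mm", and "Implant lengths will be from 8.0 up to 13.0 mm". No section requires the two implants of a patient to be the same size. Study Design assigns the technique to sites by coin toss within the patient. Study Procedures drops grafted cases from the 6-month CBCT analysis. Objectives lists the volume change from the first CBCT to the 6-month CBCT among the aims, and Hypothesis includes one on bone volume.

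**The concern.** The space the implant will occupy holds bone, and possibly marrow, in the first scan and metal in the second. A gray-range count over a box that includes this space therefore compares two different materials. Unless the space is handled identically in both scans, the computed change mixes real ridge change with a term that depends on implant size and on where the operator sets the range.

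Two things are at stake. The first is the within-site change, which is an aim in its own right and can be wrong in size or sign. The second is the precision of the comparison between techniques. The two implants of a pair may differ in diameter and length, so the extra term need not cancel within the pair. This box volume is the plan's only volume measurement for the bone-volume hypothesis.

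**Working it through.** The plan gives no volume, effect size, standard deviation, alpha or power for this endpoint, so there is no figure of its own to reproduce.

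**Inputs from the documents.** Diameters of 3.5, 4.3 and 5.0 mm and lengths of 8 to 13 mm (Surgical technique). Major/minor diameters of 3.5/3.0, 4.3/3.7 and 5.0/4.2 mm (bur chart, Figure 2). Twenty pairs (Study Procedures). For scale, a 2.83 mm crestal width gain in the narrowest ridges (Background Information).

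**Step 1: implant volume.** Treat the implant as a truncated cone with major diameter D, minor diameter d and length L. Ignore threads and internal cavity, and take the whole length as inside the box:

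V = (π·L/12) × (D² + D·d + d²)

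| Implant (mm) | Calculation | V (mm³) |
|---|---|---|
| 3.5 × 8 | π·8/12 × (12.25 + 10.50 + 9.00) | 66.5 |
| 3.5 × 10 | π·10/12 × 31.75 | 83.1 |
| 4.3 × 10 | π·10/12 × (18.49 + 15.91 + 13.69) | 125.9 |
| 5.0 × 13 | π·13/12 × (25.00 + 21.00 + 17.64) | 216.6 |

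**Step 2: what the implant space adds to a site's change.** Let s = 1 if implant voxels are counted at 6 months and 0 if not. Let f be the share of that same space counted as ridge at baseline. The contribution to 6 months minus baseline is V × (s − f). The plan fixes neither s nor f, so f is run from 0 to 1. For a 4.3 × 10 implant, in mm³:

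| | f = 0 | f = 0.5 | f = 1 |
|---|---|---|---|
| Metal excluded (s = 0) | 0 | −62.9 | −125.9 |
| Metal included (s = 1) | +125.9 | +62.9 | 0 |

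The term is zero only when s = f.

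**Step 3: scale against a real change.** Assume a width gain that falls linearly to zero at 10 mm depth, in a box 5 to 7 mm wide mesiodistally. The added volume is 0.5 × gain × 10 × box width. A 1 mm crestal gain is then 25 to 35 mm³, and 2.83 mm is 71 to 99 mm³. With metal excluded and f = 0.5, a 4.3 × 10 site with a true 1 mm gain would read between 25 − 62.9 = −37.9 and 35 − 62.9 = −27.9 mm³, an apparent loss. For this implant and gain, the sign reverses once f exceeds 25/125.9 = 0.20 to 35/125.9 = 0.28.

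**Step 4: within a pair.** The implant-volume difference is 125.9 − 83.1 = 42.8 mm³ for 4.3 versus 3.5 at 10 mm. It cannot exceed 216.6 − 66.5 = 150.1 mm³. If f is alike at the two sites, each difference is multiplied by (s − f).

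**Step 5: noise in the paired comparison.** Assume sizes vary independently within pairs, with three diameters and lengths of 8, 10, 11.5 and 13 mm equally likely. The pair difference in V then has mean 0 and SD 61.4 mm³. With 20 pairs its standard error is 61.4/√20 = 13.7 mm³. Assuming a two-sided 0.05 test, 80% power and the normal approximation, this noise alone implies a detectable mean difference of (1.96 + 0.84) × 13.7 × |s − f|. That is about 10, 19 and 38 mm³ at |s − f| = 0.25, 0.5 and 1.

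**Step 6: after the fix.** If the implant space is removed from both scans, or filled in both, s = f for every implant. The contribution is 0 mm³ at each site and 0 between sites.

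**The case against.** The strongest reply is that the plan counts segmented alveolar process, not everything in the box, and leaves the gray range open; a gap in detail is not a wrong result. If metal is counted at 6 months and the same space was counted at baseline, the term is zero. Metal lying inside a genuinely expanded ridge also belongs to the new ridge envelope, so not all of a positive term is error. Sites left with a thin buccal plate are grafted, and grafted cases leave the CBCT analysis, which limits how much metal could stand outside bone on that side. Allocation is by coin toss within the patient, and implant selection is listed as pre-surgical planning, so the expected size imbalance between techniques is zero if size is chosen independently of technique.

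Most of this stands, and it limits the point. A reader might infer that the volume change simply contains the implant's volume. The text does not say so: the term may be negative, zero or positive. A reader might also infer that the techniques differ artificially whenever the two implants differ in size. That does not follow either, because the term vanishes when s = f and random allocation removes the expected imbalance.

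What does not stand is that this is only missing detail. Metal is not alveolar process, so the natural reading excludes it, and following the rule then subtracts replaced bone from every site where that bone was counted at baseline. Nothing in the plan makes the two counts agree. Randomisation does not correct the within-site change, and it leaves the noise in the paired test.

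**Conclusion.** The point holds as a defect in how a secondary endpoint is measured. The stated rule gives a true ridge-volume change only if the implant space happens to count equally in both scans. Otherwise each site's change is off by up to the implant's volume, about 67 to 217 mm³ under the truncated-cone approximation, in a direction set by an unstated gray range. This can equal or exceed a plausible ridge gain, although that comparison rests on an assumed box width and gain profile.

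For the comparison between techniques, the supported consequence is added noise and possible chance imbalance in at most 20 pairs. An example is 43 mm³ for a 4.3 versus 3.5 pair at 10 mm, scaled by the unequal share. Systematic bias would require technique to influence implant size. The documents do not show that, and they do not state the order of implant selection and coin toss. The caliper primary outcome and the 2-D CBCT width analysis do not depend on counting implant voxels and are unaffected. The change should be made, but the trial's main result does not hang on it.

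**What to change.** Choose one of two methods before the scans are read and state it in the 3-D item.

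- Implant mask: after superimposition, copy the implant outline from the 6-month scan to the baseline scan and remove that region from both volumes. This measures change in the bone around the implant.
- Outer contour: measure the volume inside the outer ridge contour in both scans, with the implant space filled in both. This measures change in the ridge as a whole.

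With either method, use the same box size and position for both scans of a site, not only the same shape, and fix the gray-value limits in advance for all scans and sites. Report implant diameter and length by pair, so that any remaining size difference is visible.

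The cost is extra software steps on scans already planned, with no added visits or radiation. A thin zone of metal artefact next to the implant may also have to be masked in both scans, which gives up some information at the implant surface.
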